Don't Throw Your Heart Away: Medical Student Study 2

NCT04176796

Last IRB Approval Check-in: January 10 2024

Study Information

Title

Heart Transplant Tradeoff Study: 2-Condition Medical Student Study

Authors

Description

Publicly available outcome assessments for transplant programs do not make salient that some programs tend to reject many of the hearts they are offered, whereas other programs accept a broader range of donor offers. We use empirical studies to test whether transplant center performance data (i.e. transplant and waitlist outcome statistics) that reflect center donor acceptance rates influence laypersons to evaluate centers with high organ decline rates less favorably than centers with low organ decline rates. 125 medical student participants will be recruited from University of Pittsburgh School of Medicine and randomized to one of two different information presentation conditions. Participants will be given an introduction to the donor organ match process, then asked to view the table of transplant outcomes corresponding to the condition they were randomized to. Each participant is asked to choose which hospital is higher performing upon being given a choice between two hospitals: one hospital with an non-selective, "accepting" strategy (takes all donor heart offers), and one hospital with a more selective, "cherrypicking" strategy (tends to reject donor offers that are less than "excellent" quality). In order to identify the decision process that underlies this choice pattern, we will examine a putative mediator. Specifically, participants will be asked to rate the extent to which they considered patients' chances of getting an excellent heart, avoiding a less-than-optimal heart, and getting any type of heart when making their choice between the two hospitals.

Hypotheses

Hypothesis 1 When centers must present information on their transplant success rate only, lay evaluators will respond by selecting hospitals with higher transplant success. However, if information presented on transplant outcomes is stratified by the number and quality of donors used, or displayed in addition to total survival rates, then participants will respond by selecting hospitals with higher organ acceptance rates rather than the hospital with higher transplant outcomes. Hypothesis 1a: Preference for the non-selective transplant center will be lower (than for the selective center) in condition 1 (baseline: combined transplant survival only), compared to condition 2. That is, a higher proportion of participants will prefer the non-selective center over the selective center in condition 2, relative to condition 1. Hypothesis 1b: There will be a main effect of viewing stratified transplant survival, such that in condition 2 (when transplant survival is stratified by number and quality of donor hearts accepted at each center) participants will prefer the non-selective center over the selective center, relative to the baseline condition 1. Hypothesis 2 There will be an indirect (mediated) effect of providing participants with information about stratified transplant survival; this information will lead to higher preference for the non-selective hospital by leading participants to think that the chances a patient at either hospital will "get a heart at all" is a more important factor in their decision (about which hospital is a better choice for patients). Specifically ratings of importance

(0-100 continuous scale) for the item "likelihood of getting any heart" will differ across conditions 1-2 such that "getting any heart" will be rated lower in condition 1 than in condition 2. Furthermore, ratings on this item will be associated with choice, such that higher ratings will be associated with choice of the non-selective center.

Design Plan

Study type

Experiment - A researcher randomly assigns treatments to study subjects, this includes field or lab experiments. This is also known as an intervention experiment and includes randomized controlled trials.

Blinding

- For studies that involve human subjects, they will not know the treatment group to which they have been assigned.

Is there any additional blinding in this study?

n/a

Study design

We have a between-subjects design in which participants are randomized to one of two information conditions (independent variable). In each condition, they make a choice (dependent variable) between two hospitals (one with a non-selective donor acceptance strategy, and another with a more selective donor acceptance strategy). Independent variables: (1) Condition 1 ("baseline" condition): view only combined transplant survival (e.g. transplant survival rate not stratified by number and quality of donor hearts accepted at each center) (2) Condition 2: view only stratified transplant survival (e.g. transplant survival rate stratified into patients who received excellent donor organs and patients who received less than optimal donor organs) These two conditions will be analyzed for our primary analysis: a 1x2 design with 2 arms (control arm or combined transplant survival, and experimental arm or stratified transplant survival).

Randomization

We will use simple randomization, where each participant will be randomly assigned to one of the two predetermined conditions. The Qualtrics randomizer function will be used for randomization into a condition.

Sampling Plan

Existing Data

Registration prior to creation of data

Explanation of existing data

n/a

Data collection procedures

125 medical student participants will be recruited from University of Pittsburgh Medical School. Participants will be recruited via (1) an email to the Class of 2020, Class of 2021, and Class of 2022 listserv pages, and (2) a Facebook post on the class Facebook pages for the classes

corresponding to the listservs described. Inclusion criteria: Participants who are 2nd, 3rd, or 4th year medical students at University of Pittsburgh School of Medicine will be asked to participate if they confirm the following inclusion criteria in the consent form. (1) 18 years of age or older (2) must read and understand the information in the consent form (3) must want to participate in the research and continue with the survey (4) must live in United States Payment: Participants will be entered into a lottery for completing the survey and providing an email (the latter is optional). The lottery gives a 1 in 60 chance of winning a \$50 Amazon gift card and a 1 in 10 chance of winning a \$5 Starbucks gift card.

Sample size

Our target sample size is 125 participants. We expect that this will amount to approximately 60 participants per condition, although due to the nature of the randomization technique used (Qualtrics randomizer function), we may end up with slightly more or slightly less than 60 per condition.

Sample size rationale

A sample size of 61 per group was calculated to yield at least 90% power to detect a 30 percentage point difference between conditions (e.g., 35% vs. 65%) with $\alpha=0.05$ (GPower 3.1.9.4).

Stopping rule

We will stop data collection after the first of the following three scenarios is achieved: (1) 125 responses collected (2) January 20, 2020 and at least 100 responses collected (3) March 31, 2020

Variables

Manipulated variables

We will manipulate how transplant center outcomes are presented. Different components of the same outcome statistics for two transplant centers will be varied over two different conditions. (1) Condition 1 ("baseline" condition): view only combined transplant survival (e.g. transplant survival rate not stratified by number and quality of donor hearts accepted at each center) (2) Condition 2: view only stratified transplant survival (e.g. transplant survival rate stratified into patients who received excellent donor organs and patients who received less than optimal donor organs) The two conditions will be included in our main analysis, which is a 2x1 design with 1 factors (transplant survival) and 2 levels per factor: "combined": reference level, in which transplant survival rate is not stratified by number and quality of donor hearts accepted at each center "stratified": transplant survival rate stratified into patients who received excellent donor organs and patients who received less than optimal donor organs

Measured variables

The outcome variable will be a binary choice between two hospitals: one with a selective donor-heart acceptance strategy and one with a non-selective donor heart acceptance strategy. Participants will respond to the question "Which Hospital do you consider to be higher performing? Please click on one of the two tables below to indicate which hospital is the better

choice." Participants will choose between two outcome tables featuring the selective and non-selective hospital (counterbalanced, such that each of the two choices is equally likely to be presented at top of the choice scenario in each condition). The number of participants that choose each hospital will be the measured outcome variable used in analyses. On the next page of the survey, participants will respond to three mediator questions: "There are many reasons why one transplant hospital might outperform another. Which reasons were most important in your decision? Please move the slider to indicate how much you considered each of the reasons below (0=reason was not important, 100=reason was extremely important)." Participants will then move a slider bar (0-100) to indicate the importance of the following three items: (1) Patients were more likely to receive an excellent donor heart at the hospital I picked. (2) Patients were less likely to receive a marginal donor heart at the hospital I picked. (3) Patients were more likely to receive any kind of heart at the hospital I picked. The third item (more likely to receive any kind of heart) will be the only variable that is included in the planned mediation analysis.

Indices

No response

No files selected

Analysis Plan

Statistical models

To test Hypotheses 1a /1b, we will use a binomial logistic regression analysis. The categorical independent variable will be 'stratified transplant survival'; the dependent variable is binary choice of hospital. -We will test whether the main effect of "stratified transplant survival" is statistically significant and in the predicted positive direction. To test Hypothesis 2, we will conduct a causal mediation analysis to determine whether information display had a mechanistic effect on hospital choice through our proposed mediator. We will estimate the average causal mediation effect (ACME), average direct effect (ADE), and the total effect. The ACME is the effect of the experimental information display condition (stratified) on the outcome of hospital choice (selective vs. non-selective), mediated through the hypothesized mediator (the importance of "getting any heart" at each hospital when considering the choice). The remaining effect of information display on hospital choice that is not mediated through the hypothesized mediator represents the ADE. The entire effect of the information display on hospital choice via the hypothesized mediator and the direct effect is the total effect. The proportion of the total effect that is accounted for by the ACME is called the proportion mediated.{Imai, 2010}. Analyses will be performed using the "mediation" package in R (The R Foundation for Statistical Computing).{Tingley, 2014}. We will generate 95% confidence intervals by using 1000 bootstrap simulations. The unstandardized point estimate of the ACME and its 95% confidence intervals will be interpreted. -A significant ACME for "stratified transplant survival" would suggest that stratifying transplant survival by number and quality of accepted donors works via increasing the perceived importance of "getting any heart" to increase preference for the non-selective hospital. If the ACME is non-significant, we will identify where the causal path breaks down.

No files selected

Transformations

Logistic regression analysis: The categorical predictor "transplant survival stratified" will be dummy coded (0=not stratified, 1=stratified), with 'stratified' as the reference category. The outcome variable "choice of hospital" will be dummy-coded (0=selective hospital, 1=non-selective hospital). The reference category is 'selective hospital'. Mediation analysis: The categorical predictor "transplant survival stratified" will be dummy coded (0=not stratified, 1=stratified), with 'stratified' as the reference category. The continuous mediator variable "get any heart" will be mean-centered for each analysis. The outcome variable "choice of hospital" will be dummy-coded (0=selective hospital, 1=non-selective hospital). The reference category is 'selective hospital'.

Inference criteria

We will use the standard $p=0.05$ criteria for determining if the results are significantly different from those expected if the null hypothesis were correct.

Data exclusion

Two attention checks will be used. The data will be analyzed with all participants, and with only the participants who pass both of these attention checks.

Missing data

If a participant does not complete the entire survey, they will not be included in the analysis.

Exploratory analysis

No response

Other

Other

No response

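### Does Hypothesis 1 claim which hospital is chosen under each display, when the plan tests only a shift between displays?

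*Combined protocol and SAP*

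**What the plan says.** The Description gives the aim as testing whether performance data that reflect donor acceptance rates "influence laypersons to evaluate centers with high organ decline rates less favorably than centers with low organ decline rates".

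Hypothesis 1 opens with two sentences, one per type of display. With transplant success alone, "lay evaluators will respond by selecting hospitals with higher transplant success". With stratified outcomes, "participants will respond by selecting hospitals with higher organ acceptance rates rather than the hospital with higher transplant outcomes".

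Two labelled sub-hypotheses follow. Hypothesis 1a ends by explaining itself: "a higher proportion of participants will prefer the non-selective center over the selective center in condition 2, relative to condition 1". Hypothesis 1b is a main effect of the stratified display, also relative to condition 1.

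Under Statistical models: "To test Hypotheses 1a /1b, we will use a binomial logistic regression analysis". The criterion is that the main effect of stratification "is statistically significant and in the predicted positive direction".

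Under Sample size rationale, 61 per group is to give "at least 90% power to detect a 30 percentage point difference between conditions (e.g., 35% vs. 65" per cent), with alpha 0.05.

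Under Measured variables, the outcome used in the analyses is the number of participants choosing each hospital. The only confidence intervals named in the plan belong to the mediation analysis for Hypothesis 2.

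**The concern.** A between-condition coefficient says that choice moved. It does not say where choice started or ended. The share choosing the non-selective hospital could rise from 15% to 45%. The coefficient would then very probably be significant and positive, while most participants in the stratified arm still chose the selective hospital. Likewise, a rise from 55% to 85% would leave a baseline arm that already favoured the non-selective hospital.

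The opening sentences of Hypothesis 1 seem to promise more: one hospital selected under one display, the other under the other. If that is the claim, the plan names no estimate with uncertainty to support it. A significant coefficient could then be reported as proof that participants selected the non-selective hospital. What is at stake is the wording of the conclusion; the validity of the primary test is not in question.

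**Working it through.** **1. The plan's own figure.** Inputs from Sample size rationale: 35% against 65%, alpha 0.05, 90% power. Two-sided testing is assumed, since the plan does not state sidedness. Power of Fisher's exact test is the sum, over all pairs of counts (x1, x2), of Bin(x1; n, 0.35) × Bin(x2; n, 0.65) where p ≤ 0.05. At n = 60 this is 0.892; at n = 61 it is 0.9007. So 61 is the smaller-arm size at which 90% is reached, and the sample size was set for the between-condition contrast.

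**2. Hypothesis, test and sample size side by side.**

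| Place | Quantity |
|---|---|
| Hypothesis 1a | p2 > p1, where p is the proportion choosing the non-selective hospital |
| Hypothesis 1b | Effect of stratified display relative to baseline |
| Statistical models | Sign and significance of the coefficient for stratification |
| Sample size rationale | p2 − p1 = 30 points |

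All four concern the same contrast. No place in the plan mentions 50%, a majority or a within-condition test. Reading the opening sentences as p2 > 50% and p1 < 50% is an assumption brought to the text.

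**3. The aim in the Description.** It asks whether the data shown influence evaluations. That is a causal question about the display, and a randomized comparison of two displays answers it.

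**4. What the planned model already yields.** With one 0/1 predictor the model is saturated: logit(p1) = b0 and logit(p2) = b0 + b1. Take 21/61 and 40/61, the counts closest to the plan's example:
- b0 = ln(21/40) = −0.644
- b1 = ln(40/21) − ln(21/40) = 1.289, so the odds ratio is 3.63
- fitted p2 = 1/(1 + e^(−0.644)) = 0.656 = 40/61

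Both arms' proportions come back exactly. An exact 95% interval follows from each count alone: 22.7% to 47.7% for 21/61 and 52.3% to 77.3% for 40/61.

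**5. How often test and literal wording would part.** Exact enumeration at 61 per arm. Significant means Wald p < 0.05 with a positive coefficient (Fisher where a cell is zero). The third column is P(significant, observed p1 < 50% and observed p2 > 50%) divided by P(significant). Only the first row uses rates given in the plan; the others are assumptions that keep the 30-point difference.

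| True rates | P(significant, positive) | Of these, both observed shares on the predicted sides |
|---|---|---|
| 35% vs 65% | 92.9% | 0.9254/0.9293 = 99.6% |
| 30% vs 60% | 93.1% | 97% |
| 25% vs 55% | 93.4% | 83% |
| 20% vs 50% | 94.4% | 53% |
| 15% vs 45%, or 55% vs 85% | 96.2% | 22% |
| 10% vs 40% | 97.9% | 6% |

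**6. A firm contradiction is rarer.** The third column counts observed shares, which can fall on the other side of 50% by chance. A clear contradiction in the stratified arm needs its exact 95% interval wholly below 50%. At 35% vs 65%, the probability of that together with a significant result is 2.2 × 10⁻⁸. As a share of significant results it is 0.04% at 25% vs 55%, 0.9% at 20% vs 50% and 7.9% at 15% vs 45%.

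**The case for a change.** The strongest case is that the plan's rates are only an example. The target is a 30-point difference wherever it lies. At 15% vs 45% or 10% vs 40% the test would nearly always succeed, while the literal opening sentence would usually be false. Counts of 9/61 and 22/61 illustrate this: odds ratio 3.26 (95% CI 1.35 to 7.86), p = 0.0085, with an exact interval for the stratified arm of 24.2% to 49.4%. The objection adds that counts without intervals can mislead, since a share of about 65% in 61 people carries roughly 12 points either way. The two passages on coding also disagree: Manipulated variables makes the combined display the reference level and Transformations makes it the stratified one, so the intercept may be misread.

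Part of this stands. The arithmetic is right, no per-condition interval is written down, and the opening sentences are looser than 1a and 1b. It does not amount to an error, for three reasons. The example just given (14.8% vs 36.1%, a 21-point difference) still satisfies 1a and 1b, which are the hypotheses the plan says it tests. The interval is routine and comes from two counts the plan already makes its outcome. The disagreement over the reference level cannot hide an arm's share, because Transformations fixes the 0/1 codes and the counts identify each arm.

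Nor would formal intervals settle the literal claim. At 35% and 65% with 61 per arm, an exact interval excludes 50% only from 39/61 upward (or, by symmetry, from 22/61 downward). The probability is 62.6% per arm and 0.626² = 39% for both.

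**Conclusion.** The concern does not hold. The opening of Hypothesis 1 is a narrative lead-in that 1a and 1b make precise, and the test and the sample size match that precise form. Followed as written, the plan gives a sound answer to its stated question, and each arm's share can be read from the declared outcome.

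At the plan's example rates, a significant result would disagree with even the majority reading in about 0.4% of cases (100% − 99.6%). The larger figures depend on rates that are not in the plan and on a 50% threshold it never states. Printing each condition's proportion with its interval is good reporting practice, and its absence from the text is missing detail.

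This rests on two-sided testing, 61 per arm and independent responses.

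### Table order is counterbalanced by design but left out of both planned models; adding it to the Hypothesis 1 model is an optional, nearly free improvement

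*Combined protocol and SAP*

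**What the plan says.** Measured variables describes how the two tables are shown: "counterbalanced, such that each of the two choices is equally likely to be presented at top of the choice scenario in each condition". It gives no reason for this, and does not say whether order is drawn independently for each participant or forced to be even within condition. Simple randomisation is stated only for the display condition: "We will use simple randomization, where each participant will be randomly assigned to one of the two predetermined conditions".

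None of the sections on analysis uses order:

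- Statistical models, for Hypotheses 1a/1b: "The categorical independent variable will be 'stratified transplant survival'; the dependent variable is binary choice of hospital".
- Manipulated variables describes the main analysis as a "2x1 design with 1 factors (transplant survival) and 2 levels per factor".
- Measured variables, on mediation: "The third item (more likely to receive any kind of heart) will be the only variable that is included in the planned mediation analysis". In context this picks one of three rating items, but no covariate is named there or anywhere else.
- Transformations codes only condition, mediator and choice.
- Nor is order taken up as exploratory: "Exploratory analysis No response".

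**The concern.** Order is a second factor that the design controls. If it influences which table is clicked, leaving it out of the model has two consequences. The variation it causes stays unexplained. And if order is drawn independently for each participant, a chance difference between arms in the share seeing the non-selective hospital on top goes uncorrected.

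What is at stake is a little power for Hypothesis 1 and protection in the minority of studies where order happens to be uneven. Prespecification also matters. An order adjustment added after an imbalance has been seen would be a post hoc choice and open to challenge.

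**Working it through.** **Inputs from the document.** Choice rates of 35% and 65%, and 61 per group for at least 90% power (Sample size rationale). Target of 125 (Sample size). A stop at 100 or more is allowed from January 20, 2020 (Stopping rule). Simple randomisation of condition (Randomization). Significance level: "We will use the standard $p=0.05$ criteria" (Inference criteria).

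**Assumptions.** Two-sided testing, since sidedness is not stated. Order odds ratios (OR) of 1, 2, 3 and 5, since the documents give none. Marginal choice rates stay at 35% and 65% whatever the order effect.

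**Step 1: reproduce the plan's figure.** The plan says: "A sample size of 61 per group was calculated to yield at least 90% power to detect a 30 percentage point difference between conditions". For the Wald test of the log odds ratio:

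- log OR = 2 × ln(0.65/0.35) = 1.238, so OR = 3.4
- n per group = (1.96 + 1.2816)² × 2 / (0.35 × 0.65 × 1.238²) = 60.3, rounded up to 61

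Fisher's exact test also first reaches 90% at 61 (89.2% at 60, 90.07% at 61). The plan's figure is confirmed.

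**Step 2: average power with and without order.** Studies were simulated with condition and order each drawn 50:50. The models were choice ~ stratified and choice ~ stratified + position, with a Wald test at 0.05. Each cell used at least 20,000 studies, so small differences between the unadjusted figures are simulation noise.

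| N | Order OR | Unadjusted | Adjusted | Change (points) |
|---|---|---|---|---|
| 125 | 1 | 92.6% | 92.4% | -0.2 |
| 125 | 2 | 92.3% | 92.8% | +0.5 |
| 125 | 3 | 92.3% | 93.7% | +1.4 |
| 125 | 5 | 92.2% | 95.2% | +3.0 |
| 100 | 1 | 86.2% | 85.8% | -0.4 |
| 100 | 2 | 85.8% | 86.2% | +0.4 |
| 100 | 3 | 86.4% | 88.2% | +1.8 |
| 100 | 5 | 86.1% | 89.9% | +3.8 |

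Under a 50%/50% null at N=125, type I error of the unadjusted test was 4.9% to 5.0% at order ORs of 1 to 3.

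**Step 3: chance imbalance under independent draws.** With about 62.5 per arm, the difference between arms in the share seeing a given table on top has

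- SD = √(0.25/62.5 + 0.25/62.5) = 0.089, or about 9 points
- P(difference above 10 points) = 2 × [1 − Φ(0.10/0.089)] ≈ 26% by the normal approximation, and 27% by simulation

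The error this puts into the risk difference is roughly the order shift times the imbalance. A 20-point shift gives an SD of 0.20 × 9 = 1.8 points.

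In about half of these studies (about 14% of all) the imbalance runs against the hypothesis. Power there is about 88% unadjusted versus 93% adjusted at OR 2, and about 85% versus 93% at OR 3.

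**Step 4: order exactly balanced within condition.** The imbalance of Step 3 disappears. The unadjusted test becomes slightly conservative: type I error is about 4.1% at OR 3, against 4.9% adjusted. Adjustment gains about 0.3 to 0.9 points of power at ORs of 2 to 3.

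The effect on the mediation estimate was not computed, because the documents give neither a mediator effect nor its standard deviation.

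**The case against.** The case against acting is strong on size.

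- **Average gain.** It passes one point only when table order matters about as much as the intervention, whose planned contrast is itself an OR of 3.4. No order effect is documented, and planned power already exceeds 90%. This stands.
- **Mechanism.** The imbalance figure needs independent draws, and the text says only that order is counterbalanced. This stands too, although Step 4 shows a small benefit under exact balance.
- **Cost.** With no order effect, adjustment loses a little power. Holding the arms at exactly 61 each makes the loss look larger (93.0% to 92.2%), but the plan uses simple randomisation, under which it is about 0.1 to 0.2 points at 125 and up to about 0.5 at 100. The adjusted odds ratio is also conditional on position: at a 20-point shift the median log OR is about 1.32 adjusted versus 1.24 unadjusted. That change of estimand is real and should be reported.

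A reader might infer that the omission biases or invalidates the Hypothesis 1 test. The documents do not support this: order is counterbalanced within each condition, and overall type I error is not inflated.

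A reader might also infer that order confounds the mediation analysis and that conditioning on it would cure this. On the path of interest, order reaches the rating only through choice, because the rating comes on the next page and asks about the hospital already picked. A position term does not remove the difficulty that the rating follows the choice.

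**Conclusion.** Table order is controlled in the design and absent from the analysis. Including it is optional and nearly free; leaving it out is not an error. Under the plan's allocation and the assumed order effects, the average change in power at 125 runs from about -0.2 points (OR 1) to about +3 points (OR 5). The better argument is protection in a study where order happens to be uneven. There the difference is about 5 points of power at OR 2 and about 8 at OR 3, but this applies only if order is drawn independently.

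The conclusion rests on assumed order effects, marginal rates of 35% and 65%, and two-sided testing. No gain is claimed for Hypothesis 2.

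**What to change.** - In Measured variables, state how order is assigned (independent 50:50 draw or even within condition), and export the displayed order with the data.
- In Statistical models, prespecify the Hypothesis 1 model as choice ~ stratified + position, where position = 1 if the non-selective hospital is on top and 0 otherwise. Add the coding to Transformations.
- Report the unadjusted model alongside, noting that the adjusted odds ratio is conditional on position.
- Optionally, add position as a covariate to the mediator and outcome models, without presenting this as a remedy for the rating following the choice.

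The cost is a few lines of text, one extra model parameter and one exported variable. The downside is a power loss of up to about 0.5 points if order has no effect, and a conditional rather than marginal odds ratio in the adjusted model.

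### Hypothesis 2's only analysed mediator is rated after the hospital choice and about the hospital picked, so the planned mediated effect cannot separate mediation from the choice shaping the rating

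*Combined protocol and SAP*

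**What the plan says.** Under Measured variables, participants first choose the hospital they consider higher performing. Then: "On the next page of the survey, participants will respond to three mediator questions". The stem asks them to "indicate how much you considered each of the reasons below" on a 0–100 slider. The third item reads "Patients were more likely to receive any kind of heart at the hospital I picked", and it "will be the only variable that is included in the planned mediation analysis".

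Hypothesis 2 puts the mediator differently. The stratified display is to make participants give more weight to "the chances a patient at either hospital will" get a heart at all, and that weight is to move the choice. It also predicts that higher ratings go with choosing the non-selective center.

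Statistical models describes the mediator as the importance of getting any heart at each hospital. It presents the analysis as a test of mechanism, and takes a significant ACME to suggest that the display works through this rating. A non-significant ACME leads to a search for the point at which the causal path fails.

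The Description hedges in general terms ("we will examine a putative mediator"). No section mentions that the choice might influence the rating, and the fields for exploratory analysis and other matters are empty.

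**The concern.** The ACME needs a direction: display to rating, then rating to choice. Randomization protects the effect of display on choice and of display on rating. It does not protect the link from rating to choice. Here the rating is given after the choice, so people may rate highly whatever justifies the choice they have just made.

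The item wording can add to this. It refers to a different hospital depending on the answer to the outcome question. The Description defines the non-selective hospital as one that "takes all donor heart offers" and the selective one as one that "tends to reject donor offers that are less than" excellent. A participant who can see this, weighs the chance of any heart and still picks the selective hospital has no fitting way to give a high rating. This applies at least in condition 2, where the display is stratified by donor number and quality.

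At stake is the conclusion on Hypothesis 2 and the proportion mediated. The stated rule could report a mechanism that is absent, or miss one that is present.

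**Working it through.** **The plan's own figure.** The plan gives 61 per group for at least 90% power, 35% versus 65%, α=0.05. Exact enumeration of a two-sided Fisher test at 61 per group gives power 0.9007, so the figure reproduces. It concerns Hypothesis 1 and is not in dispute.

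**Inputs from the documents.** n=125, simple randomization to two conditions, 35% versus 65% choosing the non-selective hospital, 95% bootstrap interval with 1000 draws.

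**Assumptions, not in the documents.** Rating SD 25 within choosers. A gap of g points between non-selective and selective choosers, whose means are 50+g/2 and 50−g/2, clipped to 0–100. The choice does not depend on the rating, so the true ACME is zero.

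**Sign of the spurious effect.** The estimated ACME takes its sign from a×b, where a is the difference in mean rating between conditions (2 minus 1) and b is the rating–choice slope given condition. Any gap g>0 makes b positive, so a decides the sign. Ignoring clipping:

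- Gap in both arms, 35% vs 65%: a = (0.65−0.35)g = 0.30g, which is 6 or 9 points for g=20 or 30.
- Gap in both arms, 50% vs 50%: a = 0.
- Gap in condition 2 only, baseline at the selective choosers' level, 50% vs 50%: a = 50 − (50−g/2) = 0.50g, which is 10 or 15.
- Gap in condition 2 only, baseline midway (50), 35% vs 65%: a = (50−g/2+0.65g) − 50 = 0.15g, which is 3 or 4.5.
- Gap in condition 2 only, baseline at the non-selective choosers' level, 35% vs 65%: a = 0.15g − 0.50g = −0.35g, which is −7 or −10.5.

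**Hand check of the first case.** The rating variance per arm is 25² + g²×0.65×0.35, which is 716 for g=20 and 829.75 for g=30. With 62.5 per arm, SE(a) = √(2×716/62.5) = 4.79 and √(2×829.75/62.5) = 5.15. Then z = 6/4.79 = 1.25 and 9/5.15 = 1.75, and the chance that z exceeds 1.96 is about 24% and 42%. The b path hardly limits this: z ≈ 20/(25/√(125×0.2275)) = 4.3 at g=20, and more at g=30.

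**Simulation of the planned analysis.** Linear model for the rating, logistic model for the choice, percentile bootstrap. Ranges span separate runs of 200 to 1500 trials per cell; nominal is 2.5% on each side.

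| Scenario, true ACME 0 | 95% interval above 0, g=20 / 30 | Below 0, g=20 / 30 |
|---|---|---|
| Both arms, 35% vs 65% | 22–28% / 41–47% | – |
| Both arms, 50% vs 50% | 3.1% / 3.0% | – |
| Condition 2 only, low baseline, 50% vs 50% | 30–34% / 76–79% | – |
| Condition 2 only, midway baseline, 35% vs 65% | 3–4% / 11% | – |
| Condition 2 only, high baseline, 35% vs 65% | 0% / 0% | about 17% / 48% |

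(A dash means not tabulated.)

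In the first row a gap of 0 gives at most 0.1% above zero in the largest run, so the gap is the cause. The mean spurious ACME there is 0.038 or 0.075 against a total effect of 0.30, an apparent proportion mediated of 0.038/0.30 = 13% or 0.075/0.30 = 25%. Changing the SD to 20 gives 34% / 52%, and to 30 gives 17% / 33%.

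**Comparison.** Three assumed scenarios with real mediation and no dependence on the choice gave an interval above zero in 59%, 96% and 99% of trials. A significant ACME can thus arise either way.

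**The case against.** Several points on the other side have force.

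- The stem asks what was considered in the decision, so a careful respondent could report it faithfully afterwards. A non-selective chooser who gave access no weight can answer 0. This stands: the documents do not show that the choice did shape the ratings, only that the design cannot rule it out.
- A reader might infer that the wording itself builds in the predicted rating–choice association. The documents do not support this for both arms. Under Study design, condition 1 participants see only combined transplant survival, and nothing shows that they can tell which hospital yields more hearts. The wording argument is therefore confined to condition 2. In condition 1 only general rationalization after the choice remains.
- A gap between choosers is also what true mediation predicts. That is correct, and it is why the ACME cannot separate the two.
- The plan hedges: the mediator is called putative and the reading of the ACME is phrased as a suggestion. These hedges are general. Neither concerns the direction between rating and choice.
- Rating first could prime the primary outcome. That is a sound reason for the chosen order, and moving the rating is not requested.

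**Conclusion.** The concern holds for Hypothesis 2 and the proportion mediated. The order of measurement is enough to establish it, and the reference to the hospital picked adds to it at least in condition 2. A significant ACME is some evidence for mediation but does not establish it, and a non-significant one does not show where a causal path fails.

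The size is illustrative. The chooser gap, the SD and the baseline rating level have no source in the documents. Under the assumptions above, the false-positive share ranges from 0% to nearly 80%.

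Two stronger readings are tempting but unsupported. One is that the bias always favours Hypothesis 2: with a high baseline in condition 1 it runs the other way. The other is that the main result is compromised: Hypothesis 1, the total effect and the 61 per group do not use the rating and are unaffected.

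**What to change.** 1. In Statistical models, replace the claim to test a mechanism and the rule for reading a significant ACME with, for example: *Because the rating follows the choice and refers to the hospital picked, the ACME and proportion mediated will be reported as consistent (or not) with mediation but do not establish it, since the choice may have influenced the rating.* For a non-significant ACME, report the display–rating and rating–choice associations without causal-path language.
2. Only if the survey is not yet fielded, reword the mediator items so that they do not refer to the hospital picked, for example: *How important was patients' likelihood of getting any kind of heart?* The first change is still needed, because the order of measurement remains.

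The cost is a few sentences of interpretation, three item wordings if still open, and a weaker claim for Hypothesis 2. The stopping rule ends collection by March 31, 2020 and the last IRB check-in is dated January 10 2024, so the first change is probably the only one still available.
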